**PROTOCOL: HOME 2 Decolonization Study**  
**Protocol #201301035 version #1**  
**Single Site Study**

**PI: [name]., MSCI**

**Study Team Members:** **[name]**  
**[name]**  
**[name]**  
**[name]**  
**[name], BSN**  
**[name]**  
**[name]**

## **OVERVIEW**

### Background and Rationale

Community-associated methicillin-resistant *Staphylococcus aureus* (CA-MRSA) causes significant morbidity and mortality in children. There is no available vaccine against *S. aureus*. Thus, other preventive measures, including topical antimicrobial therapies, have been used in an attempt to prevent staphylococcal infections. These therapies include mupirocin (a topical antibiotic with activity against MRSA) and chlorhexidine (a topical antiseptic which is available as a medicated liquid soap as well as impregnated in cloths for sponge baths). In addition to traditional interventions (e.g., mupirocin or chlorhexidine), bathing in dilute bleach water has also been prescribed to patients with recurrent CA-MRSA infections. For the present study, we will utilize a decolonization regimen of mupirocin, dilute bleach water baths, and hygiene education. Our objective is to assess the effectiveness of decolonization measures when performed by individuals with a history of skin and soft tissue infection (SSTI) in the prior year (individualized approach) compared to decolonization of all household members (household approach) in reducing the incidence of recurrent SSTI. We hypothesize an individualized decolonization approach will be equally as effective as decolonization of all household members to prevent SSTI. The information we learn from this study may help us develop inexpensive and readily available interventions to prevent *Staph* infections.

### Objectives

1. Compare the effectiveness of decolonization of individuals with a history of skin and soft tissue infection (SSTI) in the prior year (individualized approach) to decolonization of all household members (household approach) in reducing the incidence of recurrent SSTI.
2. Test whether or not application of mupirocin to the anterior nares twice daily for 5 days will result in a higher prevalence of colonization with mupirocin-resistant strains at subsequent longitudinal samplings.
3. Determine the role of environmental contamination and household characteristics in household CA-MRSA transmission. We will quantify the baseline burden of household MRSA colonization by culturing twenty-one frequently handled household surfaces and objects.

Potential Contribution: Decolonization measures are costly and inconvenient. Therefore, targeting only household members at greatest risk for recurrent SSTI would decrease the burden and cost of performing these measures, and increase adherence to the protocol. Evaluating decolonization of all household members compared to decolonization of only those individuals experiencing SSTI in the prior 12 months, will inform prevention strategies for both specialists and primary care physicians. If we find that an individualized approach is not inferior

to a household approach to decolonization, we will design a study for dissemination and implementation of this practice, partnering with the practice-based research network, Washington University Pediatric and Adolescent Ambulatory Research Consortium (WU PAARC). If we determine that decolonization is successful in preventing SSTI, but observe an increasing incidence in mupirocin resistance over the study, we will evaluate the effectiveness of decolonization utilizing only topical solutions (e.g., dilute bleach or chlorhexidine) without application of intranasal mupirocin.

## **METHODS**

Timeline: After randomization and distribution of study materials participants will have study visits every 3 months for 12 months to ascertain colonization status and development of subsequent SSTI.

Inclusion criteria: Households which participated in the "Community-Associated Methicillin-Resistant Staphylococcus aureus (CA-MRSA) Among Household Members and the Home Environment" study (HRPO 201104330). Only participants providing written, informed consent, or for whom consent is provided by a parent or legal guardian, will be included.

Exclusion Criteria: Households in which all members experienced SSTI during the 12-month natural history study will be ineligible to participate in the trial, to eliminate the bias that would be introduced if these families were randomized to the Individualized Approach arm. We will also not approach individuals who have declined contact for future studies on the HRPO 201104330 study consent form.

Procedures: The households participating in the "Community-Associated Methicillin-Resistant Staphylococcus aureus (CA-MRSA) Among Household Members and the Home Environment" (HRPO 201104330) study will be invited to enroll in this randomized trial upon completion of the 12-month follow-up period.

Randomization: Due to logistics and the use of objective outcome measures, this study will be performed as an open trial. Enrolled households will be allocated to one of two treatment groups (household vs. individualized decolonization) 1:1 randomization using the minimization method to assure balance in family size and composition (e.g., number of household members experiencing SSTI in the prior year). Minimization is a dynamic randomization algorithm that will help to ensure that treatment arms are balanced with respect to our predefined household factors as well as the number of households in each group. REDCap will be used to implement the minimization algorithm. Assignments will be generated by the REDCap program and revealed to the study coordinator immediately prior to the enrollment visit

Enrollment visit: Will take place in the participants' homes

- Time: 30-45 minutes
- The PI or research coordinator will provide standardized hygiene education curriculum regarding handling of lotions, soaps, hygiene items, and linens.
- Participants will be given instructions on how to perform the decolonization regimen (described below).
- The inside tip of the nose, armpits, and inguinal folds (groin) of each participant will be swabbed with a culture swab.
- The inside tip of the nose of dogs and cats will be swabbed with a culture swab
- Specified household surfaces will be swabbed with a culture swab (21 sites)

Decolonization regimen:

- Application of 2% mupirocin ointment (a "pea-sized" amount) to the anterior nares with a sterile cotton applicator twice daily for 5 days.
- Daily bathing (15-minute soaks) in dilute bleach water ( $\frac{1}{4}$  cup of 6-8.5% sodium hypochlorite [Clorox®, Clorox Company, Oakland, CA] per  $\frac{1}{4}$  tub of water) for 5 days.  
(participants <1 month of age will not be asked to complete the decolonization regimen)
- Participants will be given and asked to complete a "Memory Aid" to record their daily completion of the measures, ease or difficulty of completing the measures, occurrence of adverse reactions, development of new infections, and costs incurred completing the protocol.

Follow-up phone call: Each participant will be contacted by phone 7-10 days after the enrollment visit to confirm completion of the study protocol.

Follow-up visits: Will take place in the participants' homes

- Will occur 1, 3, 6, 9, and 12 months following the enrollment visit
- Time: 15-25 minutes for each visit

At the 1 month follow-up visit:

- Each participant will complete a brief survey inquiring whether they developed any infections during the interval since the prior visit
- The inside tip of the nose, armpits, and inguinal folds (groin) of each participant will be swabbed with a culture swab. There will also be a separate household survey administered inquiring about household cleaning.
- The inside tip of the nose of dogs and cats will be swabbed with a culture swab
- Specified household surfaces will be swabbed with a culture swab (21 sites)

At the 3, 6, 9, and 12 month follow up visits:

- Each participant will complete a brief survey inquiring whether they developed any infections during the interval since the prior visit
- The inside tip of the nose, armpits, and inguinal folds (groin) of each participant will be swabbed with a culture swab.
- The inside tip of the nose of dogs and cats will be swabbed with a culture swab
- Specified household surfaces will be swabbed with a culture swab (21 sites)

If at any visit during the study a participant informs us that they have had a *staph aureus* infection and sought medical care for that infection, we will obtain and verify as much information as possible about the infection, such as date, body site, if drainage surgery was required, if a culture was obtained, what the culture results were, and whether or not antibiotics were prescribed. To obtain this information we will check ClinDesk for hospital records or ask their primary care doctor to fax us any pertinent results. If the participant was seen at SLCH, the actual specimen will be collected from the microbiology laboratory and compared to other specimens we have obtained from the household and participant swabs within that family.

Presence of high-level mupirocin resistance will be assessed in all recovered MRSA strains using PCR to detect the *mupA* gene; isolates positive for the *mupA* gene (indicating genotypic

evidence for high-level mupirocin resistance) will be confirmed phenotypically by Etest (BioMerieux, St. Louis, MO).

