### **INFORMED CONSENT**

Potential participants will be identified among participants in the "Community-Associated Methicillin-Resistant Staphylococcus aureus (CA-MRSA) Among Household Members and the Home Environment Study" (HRPO 201104330). The PI or research coordinator will provide verbal information and a letter explaining the study at the 9 month follow-up visit of the observational study. After household members have discussed the study amongst themselves, enrollment will take place at the 12 month follow-up visit of the observational study.

The enrollment visit will take place in the home. After the study design and expectations have again been described to all household members, the PI and study coordinator will obtain written informed consent from each household member. Parents or legal guardians will provide written consent for all minor participants. Children of a developmentally appropriate age (typically 7 years or older) will also be asked to sign an assent document.

Two different consent forms will be used: one for the individual approach group and one for the household approach group. Participants who agree to be in the study will be given the consent form for the treatment group to which they were randomized. The reason for having two consent forms is to minimize the chance that household members in the "Individualized Approach" arm who have not experienced SSTI in the prior 12 months (and thus NOT assigned to use the decolonization measures) will use the decolonization measures provided to the "affected" household members (those with SSTI in the prior 12 months).

The study team will emphasize that study participation is voluntary and the fact that if some household members do not wish to participate in the study, this does not exclude the remainder of the household from participation.

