## **Statistical Plan**

Sample Size and Determination of Power: The expected rate of SSTI in individuals in the Household Approach group is 9% at 3 months based on one of our prior studies. An absolute difference of 10% is considered to be clinically equivalent and has been recommended for anti-infective trials; thus, 9% SSTI incidence in the Household Approach group and 19% SSTI incidence in the Individualized Approach group 3 months post-decolonization would be considered clinically equivalent. Considering the variance inflation factor due to clustering of participants within households (estimated to be 1.4 based on our prior studies), and considering 4 interim analysis for the primary outcome to be conducted under the Data Safety Monitoring Plan, a total sample of 344 participants (172 per group) or 86 total households (43 households per group) will have 80% power at alpha=0.05 to conclude that the SSTI incidence in the Individualized Decolonization Approach is not inferior to that of the Household Decolonization Approach with a non-inferiority margin of 10%. Sample size calculations were performed using PASS 11. "The Community-Associated Methicillin-Resistant Staphylococcus aureus (CA-MRSA) Among Household Members and the Home Environment" study (HRPO 201104330) will enroll 150 households (approximately 600 participants). Taking into consideration exclusion criteria, lost to follow-up and declining participation, we believe 25-35% of households will not enroll in the HOME 2 Decolonization Study, resulting in approximately 100 households enrolling in the trial. Anticipating 10% attrition from trial enrollment to the 3-month follow-up visit, we will have 90 households for analysis of the primary outcome SSTI at 3 months.

Analysis Plan: Descriptive statistics will be used to characterize the study population, the proportion of participants colonized and infected with MRSA over the course of the study, and the types and relatedness of colonizing and infecting strains recovered from participants.

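### Does checking medical records only for reported S. aureus infections with care sought undermine the 3-month SSTI comparison?

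*Combined protocol and SAP*

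**What the plan says.** The Statistical Plan (Analysis Plan) defines the primary outcome as SSTI at 3 months in all participants. Organism and medical attendance play no part in it. Non-inferiority requires the upper limit of the two-sided 95% interval for the difference to lie below 10 points.

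The Methods (Timeline) give the purpose of follow-up: "participants will have study visits every 3 months for 12 months to ascertain colonization status and development of subsequent SSTI". At every follow-up visit, "Each participant will complete a brief survey inquiring whether they developed any infections during the interval since the prior visit". The Memory Aid issued with the regimen also asks about "occurrence of adverse reactions, development of new infections, and costs incurred completing the protocol".

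The text after the visit schedule in the Methods adds a record check. When a participant reports a Staphylococcus aureus "infection and sought medical care for that infection, we will obtain and verify as much information as possible about the infection". The facts sought include date, body site, drainage surgery and "if a culture was obtained, what the culture results were, and whether or not antibiotics were prescribed".

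On blinding, the Methods (Randomization) state: "Due to logistics and the use of objective outcome measures, this study will be performed as an open trial". Participants know their arm at consent: "Participants who agree to be in the study will be given the consent form for the treatment group to which they were randomized".

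No section says whether an unverified report counts as a primary event, or what happens when records contradict a report.

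**The concern.** Three features together look troubling. First, the trigger for checking records names an organism, while the endpoint does not. A participant treated for an abscess may not know what grew, or whether anything was cultured, and on a literal reading that report is never checked. Second, the open design is defended partly by objective outcomes. That describes cultures, PCR and Etest well, but not SSTI reported by people who know their arm, some of whom know they were not assigned decolonization. Third, the treatment of unverified or contradicted reports is left unwritten.

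The stake is the non-inferiority conclusion. With a fixed absolute margin, events missed equally in both arms shrink the observed difference and make a truly inferior strategy easier to pass. The planned safeguards do not answer this directly. The comparison in participants with a prior-year SSTI cannot correct an error common to both arms, and confirmed MRSA infection is modelled over 12 months and not tested against the margin.

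**Working it through.** **Inputs.** From the Statistical Plan: 172 participants per group, variance inflation 1.4, margin 10 points, Household rate 9%, worst acceptable Individualized rate 19%. The documents give no sensitivity (Se) or specificity (Sp) for reported SSTI, so every such value below is assumed.

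**The plan's own figure.** The unpooled non-inferiority formula at 9% in both arms, one-sided 0.05 and 80% power gives 2(0.09)(0.91)(1.645 + 0.842)²/0.10² = 101.3. Then 101.3 × 1.4 × 1.224 (Pocock-type allowance for 4 looks) = 173.5, within 1% of 172. The plan states neither the one-sided 0.05 nor the Pocock allowance, and neither bears on this point. What follows uses the stated decision rule (two-sided 95% interval) and ignores interim looks.

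**Formulas.**
- Observed rate in each arm = p·Se + (1 − p)(1 − Sp).
- Effective n = 172/1.4 = 122.9 per arm.
- SE = √{[pI(1 − pI) + pH(1 − pH)]/122.9}, where I is Individualized and H is Household.
- P(declare non-inferiority) = Φ[(0.10 − d)/SE − 1.96], where d is the observed difference.

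**No error.** At 9% versus 19%, d = 0.10 and the result is Φ(−1.96) = 2.5%. At 9% in both arms, SE = 0.0365 and power = Φ(2.739 − 1.96) = 78.2%.

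| Assumed error | Observed d at true 9% vs 19% | False non-inferiority | Power at 9%/9% |
|---|---|---|---|
| Equal Se 0.95 | 0.095 | 3.3% | 80.0% |
| Equal Se 0.90 | 0.090 | 4.3% | 81.9% |
| Equal Se 0.80 | 0.080 | 7.2% | 85.8% |
| Equal Sp 0.99 | 0.099 | 2.6% | 74.6% |
| Equal Sp 0.98 | 0.098 | 2.8% | 71.3% |
| Equal Sp 0.95 | 0.095 | 3.2% | 62.9% |
| Sp 0.99, Individualized only | 0.108 | 1.6% | 68.3% |
| Sp 0.98, Individualized only | 0.116 | 1.0% | 57.4% |

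**Which rows apply.** Events enter through a survey about any infection, and the outcome definition does not require verification. A report that is not checked therefore stays in the count. The narrow trigger can leave false reports standing, which is the Sp part of the table. It cannot delete true ones. The Se rows apply only if SSTI go unreported or if unverified reports are thrown out. Widening the trigger cannot help with the first, because there is no report to follow up. The plan does not prescribe the second.

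**If the 9% is already an observed rate.** The plan takes it from an earlier study: "The expected rate of SSTI in individuals in the Household Approach group is 9% at 3 months based on one of our prior studies". Then Se 0.80 means true rates of 11.25% versus 21.25%, observed as 9% versus 17%, with false non-inferiority 6.8%. Sp 0.95 gives 3.3%. Power stays at 78.2% in both cases.

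**Would a verified-only analysis help?** It undercounts by construction. At assumed capture of 80%, 60% and 40%, a true 10-point difference appears as 8, 6 and 4 points, and false non-inferiority is 7.2%, 20.5% and 53.7%.

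**What the trigger probably means.** Body site, drainage surgery and whether a culture was taken are all things to be looked up. That fits a skin infection whose organism is not yet established, and suggests the organism name stands loosely for SSTI. The care-sought condition is unavoidable, since without care there is no record.

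**The case for a change.** The best argument for acting is that the remedy is cheap and the silence is real. At the plan's own rates there would be 344 × 0.09 = 31 to 172 × 0.09 + 172 × 0.19 = 48 SSTI by 3 months, and only those with care sought would need a records request, by a route already in use. Interim looks at this outcome are planned about four times and the investigator is one of the monitors, so an unwritten counting convention could be settled after results by arm are known.

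Nor is every pattern of false reporting harmless. If false reports fell only on the Household arm, at Sp 0.98, its observed rate would be 0.09 + 0.91 × 0.02 = 0.1082. Then d = 0.0818, SE = 0.0451, and false non-inferiority is Φ(0.403 − 1.96) = 6.0%.

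Some of this stands. Naming SSTI in the trigger would read better, and a written convention would be tidier. But the Household-only pattern reverses what one would expect in an open trial, where the members left untreated, all in the Individualized arm, have the stronger reason to report. The stopping threshold is a 50-point difference, far beyond what counting choices could create at rates of 9% to 19%. Extra record checks would also feed no stated analysis: without a rule for contradicted reports they alter no event. Asking for a rule without showing that the natural one, counting reports as made, misleads is a request for documentation. Limiting the objectivity remark to laboratory outcomes is editorial, and the open design also rests on logistics.

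**Conclusion.** No change follows. The record-check wording is literally narrower than the endpoint, but the endpoint is not tied to the record check, so the gap leaves reports unverified without losing events. On the plain reading, where reported SSTI count, equal over-reporting moves false non-inferiority from 2.5% to at most 3.2% for specificity down to 0.95. Excess reports in the Individualized arm lower it to 1.0% to 1.6%. The price is power: 62.9% in the worst equal case shown, 57.4% with 2% false positives in the Individualized arm alone. That error makes non-inferiority harder to claim.

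The inflation to 7.2% depends on under-detection that the trigger does not cause, unless analysts adopt an exclusion the plan does not contain. A verified-only sensitivity analysis would lean in the direction the concern fears.

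This rests on assumed sensitivities and specificities, a normal approximation with effective n of 122.9 per arm, no interim adjustment, and the reading that the primary count uses reports as made. It would need revisiting if unverified reports were in fact excluded. Analysts can sensibly read the trigger as any SSTI for which care was sought and apply one convention to both arms.

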### **INFORMED CONSENT**

Potential participants will be identified among participants in the "Community-Associated Methicillin-Resistant Staphylococcus aureus (CA-MRSA) Among Household Members and the Home Environment Study" (HRPO 201104330). The PI or research coordinator will provide verbal information and a letter explaining the study at the 9 month follow-up visit of the observational study. After household members have discussed the study amongst themselves, enrollment will take place at the 12 month follow-up visit of the observational study.

The enrollment visit will take place in the home. After the study design and expectations have again been described to all household members, the PI and study coordinator will obtain written informed consent from each household member. Parents or legal guardians will provide written consent for all minor participants. Children of a developmentally appropriate age (typically 7 years or older) will also be asked to sign an assent document.

Two different consent forms will be used: one for the individual approach group and one for the household approach group. Participants who agree to be in the study will be given the consent form for the treatment group to which they were randomized. The reason for having two consent forms is to minimize the chance that household members in the "Individualized Approach" arm who have not experienced SSTI in the prior 12 months (and thus NOT assigned to use the decolonization measures) will use the decolonization measures provided to the "affected" household members (those with SSTI in the prior 12 months).

The study team will emphasize that study participation is voluntary and the fact that if some household members do not wish to participate in the study, this does not exclude the remainder of the household from participation.

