had not experienced SSTI during the 12-month natural history study) may benefit from the decolonization of household contacts as the burden of CA-MRSA in the household may decrease and subsequently reduce the risk of transmission. Participants will also receive education about the *Staph* germ. This project may decrease the incidence of CA-MRSA infections, and thus reduce healthcare utilization for CA-MRSA treatment, potentially preventing additional spread of virulent CA-MRSA strains. The project findings may lead to therapeutic and/or preventive advances that will benefit a large number of patients and have a positive impact on healthcare utilization and expenditures.

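### The arm is revealed before members sign arm-specific consent forms, so entry to the primary comparison can depend on the arm, and uptake is not compared by arm

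*Combined protocol and SAP*

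**What the plan says.** **Order of events.** The Randomization paragraph under Methods states: "Assignments will be generated by the REDCap program and revealed to the study coordinator immediately prior to the enrollment visit". Minimization acts at household level, to secure "balance in family size and composition (e.g., number of household members experiencing SSTI in the prior year").

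Under Informed Consent, the investigator or coordinator "will provide verbal information and a letter explaining the study at the 9 month follow-up visit" of the parent observational study. Household members then discuss it among themselves, and enrollment follows at that study's 12-month visit. There the design is described again, written consent is taken from each member, and "Participants who agree to be in the study will be given the consent form for the treatment group to which they were randomized". The stated reason for two forms is to discourage unassigned members of Individualized households from using the products.

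**Who is included.** Members may decline singly: "if some household members do not wish to participate in the study, this does not exclude the remainder of the household from participation". The inclusion criteria add: "Only participants providing written, informed consent, or for whom consent is provided by a parent or legal guardian, will be included".

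**Analysis.** The primary outcome in the Statistical Plan is the difference in 3-month SSTI proportions over all participants. Intention-to-treat and per-protocol sets are named, but nothing says how members who decline after assignment are counted. The comparison restricted to members with prior-year SSTI is secondary.

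**Monitoring.** Under Data to be reviewed, adverse events and attrition are specified by study group. Eligibility and refusal rates (item 2a) are not. Item 2c checks baseline characteristics of randomized participants and households, including household size and the number with SSTI during the natural history study.

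**The concern.** In an open, household-randomized trial, the analysis set should be fixed before anyone whose consent is needed can know the arm. Here the form itself discloses the arm no later than signature, and inclusion depends on that signature.

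What unaffected members are asked to do differs by arm. In the Household arm they face the 5-day regimen. In the Individualized arm they face swabs at six visits (enrollment and months 1, 3, 6, 9 and 12) with no regimen. Either could prompt refusal:

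- More refusal by unaffected Household-arm members leaves that arm richer in affected members. Its SSTI proportion rises and the result moves toward non-inferiority.
- More refusal by unaffected Individualized-arm members moves the result away from non-inferiority.

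Minimization balances households at allocation, not which members later sign. Without a by-arm account of uptake, a reader of the results could not tell which of these happened, or whether either did.

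**Working it through.** **Inputs from the Statistical Plan.** Household-arm SSTI rate 9%; margin 10 points; decision by the upper limit of a two-sided 95% interval (one-sided 2.5%); variance inflation 1.4; 172 participants per group. Mean household size is 344/86 = 4, and in the parent study 600/150 = 4.

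**The plan's own figure.** At one-sided alpha 0.05 and 80% power, 2 × 0.09 × 0.91 × (1.645 + 0.842)² / 0.10² = 101.3. Multiplying by 1.4 gives 141.8, and by 1.208 for four equally spaced looks with Pocock-type spending gives 171.2, that is 172 per group. The checks below use the stated decision rule (one-sided 2.5%) without an interim adjustment, so base power is 78.2% rather than 80%.

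**Assumptions not in the documents.** A = 1 to 2 affected members (prior-year SSTI) of 4; risk ratio RR = 2 to 6 for affected versus unaffected members; only unaffected members decline; n held at 172 per group.

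**Formulas.**
- Unaffected risk r0 = 0.09 × 4 / (A × RR + 4 − A); affected risk r1 = RR × r0. This gives 2.6% to 7.2% unaffected and 12% to 24% affected.
- Rate in an arm where a fraction d of unaffected members decline = [A r1 + (4 − A)(1 − d) r0] / [A + (4 − A)(1 − d)].
- Shift = that rate − 0.09.
- If the Household arm declines (true difference 10 points): error = Φ(−1.96 + shift/SE1), with SE1 = √[1.4(0.19 × 0.81 + 0.09 × 0.91)/172] = 0.0438.
- If the Individualized arm declines (true difference 0): power = Φ((0.10 − shift)/SE0 − 1.96), with SE0 = √[1.4 × 2 × 0.09 × 0.91/172] = 0.0365.

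**Example (A = 1, RR = 6, d = 0.40).** r0 = 0.36/9 = 0.04 and r1 = 0.24. Rate = (0.24 + 3 × 0.6 × 0.04)/(1 + 1.8) = 0.312/2.8 = 0.1114, a shift of 2.14 points.

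**Results over the assumed range.**

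| Unaffected members declining | Shift (points) | Error if Household arm declines more (base 2.5%) | Power if Individualized arm declines more (base 78%) |
|---|---|---|---|
| equal in both arms | 0 | 2.5% | 78% |
| 20% vs 10% | 0.17–0.48 | 2.7–3.2% | 74–77% |
| 10%, one arm only | 0.15–0.41 | 2.7–3.1% | 75–77% |
| 25%, one arm only | 0.42–1.15 | 3.1–4.5% | 68–75% |
| 40%, one arm only | 0.75–2.14 | 3.7–7.1% | 58–72% |

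For 20% versus 10%, the shift is the difference between the two arms' rates from the same formula. If RR = 1, every shift is zero.

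**Effect of holding n fixed.** At 40% refusal with A = 1, the arm shrinks to 43 × 2.8 ≈ 120. Allowing for this, the worst error is about 6.4% instead of 7.1%. The worst power is about 45% instead of 58%, but that extra loss comes from smaller numbers, not selection.

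**The case against.** **Agreement may come before the form.** The Randomization paragraph speaks of households already enrolled being allocated. Informed Consent has months of notice, household discussion and a renewed description before those who agree receive a form. The assignment is revealed to the coordinator, not to members. On this reading the signature only documents a decision already made. This stands in part: much of the decision may indeed come early. But no record of it is described, nothing says members are unaware of the arm at that moment, and inclusion turns on the later signature.

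**The baseline check would show it.** Item 2c includes household size and the number with prior SSTI. If it is tabulated by arm among consented members, one-sided refusal could appear. At 40% refusal the affected share would move from 25% to 36% (1/2.8) with one affected member, or from 50% to 62.5% (2/3.2) with two. This also stands in part. However, the item does not compare consented with eligible members, and its household counts may describe the full roster.

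**The large scenarios are unlikely.** Candidates have already been through the parent study's follow-up, and the planned mean of 4 per household matches the parent study's. This is fair; 20% versus 10% is a more ordinary case than 40% versus none.

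**Stronger readings.** A reader might infer that the design is biased toward non-inferiority, that members do decide knowing their arm, or that refusals go unmonitored. The documents support none of these. They fix no direction, leave the timing of the decision open, and do have refusal rates reviewed, only not by arm.

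**Conclusion.** The concern holds as a gap in safeguards, not as a demonstrated bias. As written, the set of analysed members can form after allocation, and no planned comparison would show whether uptake differed by arm. Under the assumed household mix and risk ratios, a plausible difference in refusal moves the estimate by less than half a point, and strongly one-sided refusal by about 2 points. Nothing in the documents says refusal will be one-sided. These sizes rest on assumptions about composition, risk and refusal that the documents do not supply. The point is of modest importance, worth making because the remedy is cheap.

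**What to change.** 1. At the enrollment visit, after the study and both arms are described, record each member's yes or no in REDCap. Only then generate or reveal the assignment and hand out the arm-specific forms as planned. This keeps their purpose of limiting use by unassigned members.
2. Specify in the Data and Safety Monitoring Plan that refusal rates are reviewed by study group.
3. Report uptake, and refusals after assignment, by arm and prior-SSTI status against the parent-study roster. The denominators exist: "Potential participants will be identified among participants in the" parent study, and the plan already distinguishes members who "had not experienced SSTI during the 12-month natural history study".
4. State that the intention-to-treat set is consented members analysed by assigned arm.

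Optional: a sensitivity analysis of the primary comparison standardized to the pre-assignment roster by prior-SSTI status. It assumes refusal is unrelated to risk within those strata, which cannot be tested because refusers have no outcomes.

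**Cost.** Protocol and consent-process wording, and one by-arm table. Forms and supplies for both arms must be carried to every visit, the assignment must be generated or opened during it, and some refusals at signature may remain. If in-visit assignment is not feasible, the by-arm uptake report can be done alone.
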